## 10.7 Efficacy Analysis

The efficacy analysis will be performed on both the MITT and the efficacy evaluable populations. For all duration endpoints the following matrix will be used for analyses:

Population	Analysis	Description	Methods
MITT	Main Analysis	Impute duration for subjects who drop out prior to healing with a duration of 336 hours (14 days x 24 hours).	Hodges-Lehmann estimation methods; Wilcoxon rank sum test to compare arms
	Sensitivity Analysis	Subjects who drop out prior to healing will be considered censored.	Kaplan-Meier estimation methods; Log-rank test to compare arms
EE	Main Analysis	No imputation required since these are complete cases.	Hodges-Lehmann estimation methods; Wilcoxon rank sum test to compare arms

For all endpoints on the occurrence of prevention of progression, counts and percentages will be summarized, and chi-square tests, or Fisher's exact test will be used to compare arms, as appropriate. Fisher's exact tests will be used if any of the expected cell counts in the Rx C crosstabulations are less than 5.

For size endpoints, means, medians, standard deviations and ranges will be summarized. T-tests will be used to compare arms if the sizes are approximately normally distributed, or Wilcoxon rank sum tests will be used if the sizes are markedly non-normally distributed.

For the severity endpoints, counts and percentages will be summarized, and Cochran-Mantel-Haenszel tests will be used to compare the arms.

In order to assess whether there are differences among centers in treatment effects, a Cox proportional hazards model analysis of the duration of herpetic episode will also be performed for the primary duration endpoint and for both the MITT and EE populations. The model will include terms for treatment, center, and treatment by center interaction. A test will be performed to test for the significance of the interaction. This test will be conducted at the 0.10 level of significance. If the interaction is found to be significant, estimates of treatment effect will be provided by center, as well as overall.

#### **10.7.1 Duration of Classical Lesions (clinician and patient assessed)**

A classical herpetic lesion is defined as one that passes through any of Stages 3, 4 or 5 (vesicle/pustule, ulcer/soft crust, or hard crust). Therefore, all aborted lesions will be excluded from this analysis. The duration of a classical lesion is defined as the time, in hours, from the beginning of treatment to the onset of Stage 6, or, if Stage 6 is never observed, Stage 7.

#### **10.7.2 Duration of Herpetic Episode (clinician and patient assessed)**

Duration of herpetic episode is measured by assessment of treated lesion stage daily up until Stage 6 for classical lesions or Stage 7 for non-classical lesions for a maximum of 14 days, with a minimum of 3 consecutive days of assessment. For a classical lesion, the duration of the herpetic episode is defined as the time, in hours, from the beginning of treatment until the loss of hard crust (Stage 6, residual erythema can be present after loss of hard crust). A classical lesion is defined as one that progresses through any of the vesicle/pustule, ulcer/soft crust, or hard crust stages (stages 3, 4 or 5). For non-classical lesions, duration of herpetic episode is defined as the time from the beginning of treatment until complete resolution of all local signs and symptoms (Stage 7).

#### **10.7.3 Duration until Complete Healing of the Herpetic Episode (clinician and patient assessed)**

Duration until complete healing of the herpetic episode is defined as the time, in hours, from the beginning of treatment to the onset of Stage 7, for both classical and non-classical lesions. All subjects will visit the clinic daily, for a minimum of 3 days and a maximum of 14 days, until the lesion reaches Stage 7 with no signs or symptoms of a herpetic lesion.

#### **10.7.4 Prevention of Progression to Classical Lesions (clinician and patient assessed)**

A classical herpetic lesion is defined as one that passes through any of Stages 3, 4 or 5 (vesicle/pustule, ulcer/soft crust, or hard crust). Prevention of progression to classical lesions will be analyzed by comparing the proportions of subjects in each treatment group who do not display classical lesions. (These are considered aborted lesions.)

#### **10.7.5 Clinician Assessed Lesion Size**

For each subject, the subject's maximum lesion area (length x width) for ulcerative lesions during the vesicular, ulcerative, and hard crust stages will be determined. In

addition, the cumulative lesion area, for which ulcerative lesion areas, day by day, will be added. Last, the cumulative lesion area “all lesions” will be determined; for this parameter, all patients will be included (i.e. both ulcerative and non-ulcerative recurrences).

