### **7.3.3 Lesion Size Assessment**

At each clinic visit, the Investigator, or trained designee, will use a disposable ruler, supplied by the sponsor, to measure the lesion size. Two measurements will be taken: 1) the length of the longest dimension of the lesion; 2) the maximum length of the lesion dimension perpendicular to the axis of the first measurement taken.

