#### 6.1.4 Efficacy Endpoint Definitions

Definitions of the efficacy endpoints are detailed below.

**Duration of the classical herpetic lesion:** Duration is based on staging of the lesion.

Staging is graded as follows: 0=prodromal, 1=erythema, 2=papula/edema, 3=vesicle/pustule, 4=ulcer/soft crust, 5=hard crust, 6=residual swelling/dry flaking, 7=normal skin. The duration of a classical lesion is defined as the time, in hours, from the beginning of treatment to the onset of Stage 6, or, if Stage 6 is never observed, Stage 7. A classical lesion is defined as one that progresses through any of stages 3, 4 or 5.

**Duration of the herpetic episode (classical and non-classical):** For a classical lesion, the duration of the herpetic episode is defined as the time, in hours, from the beginning of treatment until the loss of hard crust (stage 6; residual erythema can be present after loss of

hard crust). For non-classical (aborted) lesions, duration is defined as the time, in hours, from the beginning of treatment until complete resolution of all local signs and symptoms (stage 7).

**Duration until complete healing of the herpetic episode (classical and non-classical):** Duration until complete healing of the herpetic episode is defined as the time, in hours, from the beginning of treatment to the onset of Stage 7, for both classical and non-classical lesions. All subjects will visit the clinic daily, for a minimum of 3 days and a maximum of 14 days, until the lesion reaches Stage 7 with no signs or symptoms of a herpetic lesion.

**Prevention of progression to a classical lesion:** Prevention of progression to classical lesions will be defined as yes for subjects who experience a classical herpetic lesion (i.e., one that passes through any of Stages 3, 4 or 5 (vesicle/pustule, ulcer/soft crust, or hard crust)) and as no for subjects with only aborted, non-classical lesions.

**Maximum lesion area of the classical lesions:** Maximum lesion area of the classical lesions is defined as the maximum lesion area (length x width) for classical lesions during the vesicular, ulcerative, and hard crust stages.

**Cumulative lesion area of the classical lesions:** Cumulative lesion area of the classical lesions is defined as the cumulative lesion area, for which classical lesion areas, day by day, will be added.

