**Cumulative lesion area of all lesions:** Cumulative lesion area of all lesions is defined as the cumulative lesion area of both classical and non-classical recurrences.

**Duration of classical herpetic lesion hard scab:** Duration of classical herpetic lesion hard scab will be defined as the assessed duration of the hard crust, stage 5, for the classical lesions. This duration will represent the onset of stage 5 until the time of classical lesion healing at stage 6 or 7, whichever occurs earlier. For lesions that bypass stage 5, duration of hard scab phase will be calculated as time between the two adjacent assessments either side of stage 5.

**Severity of lesion pain:** Pain will be evaluated based on the subject's diary, where the subject will record, just prior to each treatment and three times daily once treatment is complete, the level of pain caused by the defined lesion. The rating scale for pain assessment has four levels for severity: none (1), mild (2), moderate (3), and severe (4).

**Duration of lesion pain:** Duration of pain will be measured in hours from the time of the first occurrence of a pain level of mild, moderate, or severe until a consistent score of a pain level of none has been achieved over at least 2 consecutive pain assessments, or until the lesion is completely healed, whichever occurs first. Subjects who do not reach the no-pain level within 14 days will be considered censored immediately following their last pain assessment. Subjects who never reach a pain level of mild, moderate, or severe will be assigned a duration of pain value of 0 hours.

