### **7.13.1 Duration**

Imputation will only be used for analyses of duration endpoints and only in the MITT Population. Duration for subjects who drop out prior to healing will be imputed with a duration of 336 hours (14 days x 24 hours) for the main analyses of duration endpoints in the MITT Population. Hodges-Lehmann technique will be used for estimation and Wilcoxon rank sum tests will be used to compare the groups on duration endpoints in the MITT Population. In addition, subjects who drop out prior to healing will be considered censored in a sensitivity analysis of duration endpoints in the MITT Population and Kaplan-Meier estimation methods will be used with log-rank tests for comparison of the groups.

For analysis of duration in the EE Population, no imputation is required since these are complete cases. Hodges-Lehmann technique will be used for estimation and Wilcoxon rank sum tests will be used to compare the groups on duration endpoints in the EE Population.

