## 8 Handling of Missing Data

All missing data will be queried. Missing efficacy data on duration endpoints for subjects in the MITT Population which are not retrievable through queries will be handled using imputation of 336 days. Other missing data, including missing safety data, will not be imputed.

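### Cumulative lesion area sums only measured days with no imputation in MITT, so missed visits and early dropout shrink it and unequal dropout flatters the arm that loses more subjects

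*Protocol*

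**What the plan says.** **How area is obtained.** Protocol 7.3.3 ties the measurement to attendance: "At each clinic visit, the Investigator, or trained designee, will use a disposable ruler". A day without a visit has no area.

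**How it is accumulated.** Protocol 10.7.5 uses "the cumulative lesion area, for which ulcerative lesion areas, day by day, will be added" and adds an all-lesions version. SAP 6.1.4 has the classical version "defined as the cumulative lesion area, for which classical lesion areas, day by day, will be added" and states that "Cumulative lesion area of all lesions is defined as the cumulative lesion area of both classical and non-classical recurrences". SAP 6.1.2 lists both as secondary efficacy endpoints.

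**What happens to missing values.** SAP 7.13.1 states: "Imputation will only be used for analyses of duration endpoints and only in the MITT Population". The matrix in SAP 7.13.5 marks area as not imputed in either population, and SAP 8 closes the remaining gap: "Other missing data, including missing safety data, will not be imputed". Protocol 10.3.3 and SAP 7.1.3 restrict the EE analysis to observed values.

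**How arms are compared.** Protocol 10.7 and SAP 7.13.3 use a t-test or a Wilcoxon rank sum test on the resulting values. There is no scaling for the number of days observed. Area has no sensitivity analysis; duration has one based on censoring.

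**The contrast with duration.** In the main MITT analysis of durations, "Duration for subjects who drop out prior to healing will be imputed with a duration of 336 hours", which is the longest value the 14-day window allows.

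**The concern.** A sum over visits falls whenever a visit is missing. A subject who leaves on Day 2 with an open lesion contributes one or two early measurements and ends with one of the smaller cumulative areas in the trial. In the same MITT population, the main duration analysis gives such a subject the least favourable value, provided the lesion counts in that endpoint. So the two rules push in opposite directions for the same event.

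What is at stake is the reading of two secondary endpoints. Protocol sections 2 and 4 cite a trend on cumulative lesion size in the earlier Phase 2 study, so a positive result here would be taken as support. The arms differ in glycolic acid, and the active solution has a pH of 2.5 (Protocol 6.1), so unequal tolerability and hence unequal dropout are possible. The analysis should not depend on that not happening.

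**Working it through.** The plan states no expected value, SD or power for any area endpoint, and no dropout or missed-visit rate. There is no plan figure to reproduce. The check has three parts.

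**1. One lesion.** Assume a 7-day lesion with a peak parameter of 40 mm², with time scaled as t = (day − 0.5)/7. The area is 40 × t/0.35 while t < 0.35, then 40 × (1 − t)/0.65. Daily areas are 8.16, 24.49, 39.56, 30.77, 21.98, 13.19 and 4.40, with sum 142.5.
- Leaving after Day 2 keeps (8.16 + 24.49)/142.5 = 23% of the true sum.
- Leaving after Day 3 keeps 72.21/142.5 = 51%.
- Missing only Day 3 loses 39.56/142.5 = 28%. Linear interpolation gives (24.49 + 30.77)/2 = 27.63, which cuts the loss to (39.56 − 27.63)/142.5 = 8%.

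The peak cancels, so these shares depend only on the shape. Another assumed shape (median healing on Day 8, peak on Day 2) keeps 12%, 38% or 58% after leaving at visit 1, 2 or 3. Averaged over simulated classical lesions with the last observed day uniform before healing, a dropout keeps about 56%. Missing 5% of visits at random keeps about 95%, and interpolation restores over 99%.

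**2. Trials with no true effect.** All runs use a two-sided Wilcoxon test at 0.05, so the nominal chance of favouring a given arm is 2.5%. Dropout is unrelated to lesion size.
- *Spread dropout:* 56 classical lesions per arm (75 × 0.75 = 56.25, from the 75 treated per arm and the 25% aborted rate in Protocol 10.7.9), lognormal duration with median 7 days, lognormal peak area, last day uniform before healing, 5% of visits missed, 2,000 trials per scenario.
- *Early dropout:* 75 per arm, median healing on Day 8, lognormal peak area (SD of log 0.7), dropout uniform over visits 1-3, 1,500 trials per scenario.

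| Dropout, higher vs lower arm | Spread: significant for higher-dropout arm | Spread: difference in mean area | Early: significant for higher-dropout arm |
|---|---|---|---|
| 10% vs 5% | 3.6% | −1.8% | 4.3% |
| 15% vs 5% | 5.8% | −4.5% | 10.6% |
| 20% vs 5% | 8.7% | −6.7% | 20.1% |
| 30% vs 10% | 13.5% | −9.6% | not run |
| 30% vs 5% | 15.6% | −10.2% | not run |

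Repeat runs at 15% vs 5% under similar assumptions gave 4.8% to 5.4% for spread dropout and 9.4% to 10.9% for early dropout. With equal dropout the figure stays nominal: 2.2% at 5% vs 5% (early), and a total two-sided rejection rate of 4.3% at 10% vs 10% (spread, 75 treated per arm).

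**3. Candidate remedies, again with no true effect.**
- *Interpolate missed visits, then fill days after dropout from completers of both arms still unhealed on that day* (a single fill, spread dropout). At 15% vs 5%, significance for the higher-dropout arm falls from 5.8% to 2.1%. Total rejection is 5.5%, leaving 5.5 − 2.1 = 3.4% the other way. At 30% vs 5% the figures are 1.1% and about 5.3%, so a small reverse tilt appears when the imbalance is large. Over all five scenarios, total rejection is 5.0% to 6.4%.
- *Rank every dropout above the largest observed area* (early dropout). False significance against the higher-dropout arm is 15.9% to 18.8% at 15% vs 5%, and 34.8% to 36.8% at 20% vs 5%. This exceeds the error it would replace.

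**The case against.** **The text never says that a missed day counts as zero.** That is true, and an analyst could instead treat an incomplete sum as missing. But no document says so. Adding what was measured with no imputation is the rule as written, and its arithmetic effect is to give unmeasured days no area. If the other reading is meant, it has to be stated.

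**EE already deals with dropout.** This stands in part. Area is also analysed in EE, which excludes subjects not followed to healing or Day 14, so an MITT/EE disagreement would be visible. EE does not repair missed visits or dropout related to lesion severity, and MITT is the primary population.

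**The imbalance is assumed.** This also stands. Protocol 7.2.4 keeps anyone who made even one application in all assessment visits, so stopping treatment is not leaving the study. Protocol 7.3 asks for staffing seven days a week. Earlier studies of the formulation report mild reactions (Protocol section 2). A reader might infer that the active arm will lose more subjects and so be favoured; the documents do not support that prediction. The point is a vulnerability whose direction depends on which arm loses more.

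**The contrast with duration can be overdrawn.** A reader might infer that a dropout gets 336 hours on every duration endpoint. The documents contradict this. Pain duration is censored for subjects not pain-free within 14 days (Protocol 10.7.7, SAP 6.1.4). SAP 7.1.2 limits imputation to the primary endpoint, in conflict with SAP 7.13.1. A subject who leaves before Stage 3 is not a known classical lesion, so is not clearly part of the classical endpoints but still adds a truncated sum to the all-lesions area. Area is unimputed under either SAP section.

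**Conclusion.** The point holds for the two cumulative-area endpoints. Followed as written, the plan truncates the sum downward for missed visits and, in MITT, for early dropout. Bias between arms requires unequal dropout or unequal missed visits; with equal rates there is no inflation.

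At 15% vs 5% dropout the chance of a false significant result for the higher-dropout arm is about 5-6% to about 10-11% instead of 2.5%, depending mainly on whether dropout is spread until healing or concentrated on Days 1-3. It is smaller at 10% vs 5% and grows with the gap. Dropout rates, dropout timing and lesion shape are all assumptions.

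Only secondary endpoints are touched. The primary endpoint does not use area, and nothing here bears on it. The change should be made, but the trial's main conclusion does not depend on it.

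**What to change.** Amend Protocol 10.7.5 and SAP 6.1.4, 7.13.1, 7.13.3, 7.13.5 and 8 as follows.

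1. In MITT and EE, fill a missed visit lying between two attended visits by linear interpolation. Protocol 10.3.3 and SAP 7.1.3 bar imputation in EE, so they need a stated exception.
2. In MITT, as the main analysis, fill the remaining days of a subject who leaves before healing from subjects of both arms, pooled and blinded, whose lesions were still unhealed on the same day. Multiple imputation is preferable to a single fill. Bring SAP 7.1.2 into line.
3. Report the observed-only sum and a worst-rank analysis as sensitivity analyses. Worst rank should not be the main analysis, given the reverse error shown above.
4. State whether a subject who leaves before Stage 3 enters the classical-area analysis.

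The cost is SAP wording, a short protocol edit and a little more programming. SAP 9 allows such changes before unblinding if they are described. The price is the assumption that dropouts would have healed like comparable subjects who stayed, which the sensitivity analyses in item 3 probe.

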#### **10.7.6 Duration of the Herpetic Lesion Hard Scab (clinician and patient assessed)**

Duration of the hard scab will be defined as the assessed duration of the hard crust, stage 5, for all subjects experiencing known classical lesions. This duration will represent the onset of stage 5 until the time of classical lesion healing at stage 6 or 7, whichever occurs earlier. Only known classical lesions will be included in this analysis. For lesions that bypass stage 5, duration of hard scab phase will be calculated as time between the two adjacent assessments either side of stage 5.

#### **10.7.7 Duration of Pain (subject assessed)**

Duration of pain will be evaluated based on the subject’s diary, where the subject will record, just prior to each treatment and three times daily once treatment is complete, the level of pain caused by the defined lesion. The rating scale for pain assessment has four levels: none (1), mild (2), moderate (3), and severe (4). For each subject, duration of pain will be measured in hours from the time of the first occurrence of a pain level of mild, moderate, or severe until a consistent score of a pain level of none has been achieved over at least 2 consecutive pain assessments, or until the lesion is completely healed, whichever occurs first.

Subjects who do not reach the no-pain level within 14 days will be considered censored immediately following their last pain assessment. Subjects who never reach a pain level of mild, moderate, or severe will be assigned a duration of pain value of 0 hours.

#### **10.7.8 Severity of Lesion Pain**

The maximum severity (over time) of lesion pain will be summarized.

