
Statistical Methods: Generally, statistical hypothesis tests will be two-tailed, and statistical significance will be declared when the p-value is less than 0.05. Continuous variables will be summarized using descriptive statistics, specifically the mean, median, standard deviation, minimum and maximum. Categorical variables will be summarized by frequencies and percentages.
 
All subjects who received (at least some) treatment, whether they were formally entered into the Treatment Phase of the study or applied the test material without formal authorization, will be included in the Safety Population. The safety analysis will be performed on the Safety Population.
 
All subjects who have been entered into the Treatment Phase of the study will be included in the Modified Intent to Treat (MITT) population. The MITT population will be used as the primary analysis population. All subjects who have been entered into the Treatment Phase of the study and have been followed successfully until their lesion healed, or until 14 days, whichever is earlier, will be included in the Efficacy Evaluable population. The efficacy analysis will be performed on both the MITT and the Efficacy Evaluable populations.
 
No imputation of missing data will be performed for the efficacy analyses for the Efficacy Evaluable population.
 
The duration of the classical herpetic lesion (both clinician and patient assessed) will be analyzed using the Hodges-Lehmann method as the primary efficacy analysis method for estimating the median difference between the two arms. Duration of the herpetic episode (both clinician and patient assessed), duration of complete healing of the herpetic episode (both clinician and patient assessed), duration of the herpetic lesion (both clinician and patient assessed), duration of the herpetic lesion hard scab (both clinician and patient assessed), and duration of pain will be analyzed in the same manner as the duration of the classical lesion.
 
The proportions of subjects in each treatment group who do not display classical lesions (prevention of progression to classical lesions) will be compared using Fisher's Exact Test.
 
For pain, the maximum severity will be analyzed using the Cochran-Mantel-Haenszel Test to test for differences between treatment groups.
		

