## 7.2.5 Subject Diaries

Each subject will be instructed to record into their diaries the date and time of their first treatment, the stage of their lesion, and his or her assessments of pain as described in this section. The recording of the assessments of lesion stage and pain level are to be done three times per day, just prior to initiation of each treatment (i.e. just prior to the first application in a set of three (3) applications). After the course of treatment is completed, assessment of lesion stage and pain level will continue 3 times daily with approximately 6 hours in between each assessment until the lesion is healed. The subject will also be instructed to bring the diary to each office visit so that the Investigator or trained designee can review it.

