### 7.2.5.1 Pain Assessment

At the time of the subject's call to enter the Treatment Phase of the study, the clinic will ask the subject to provide the time of the onset of any pain caused by the herpes lesion to be treated along with the severity of any lesion pain.

The severity of lesion pain will be based on the following rating scale:

1 = None	No pain
2 = Mild	Pain is present in such a way that the subject is only vaguely aware of it and it does not interfere with daily activities
3 = Moderate	The subject is aware of pain at all times, but it does not interfere with daily activities
4 = Severe	Level of discomfort of pain is such that it interferes with daily activities.

As noted in Section 7.2.5, the subject will also record in the diary, just prior to each treatment, the severity of any lesion pain. After the course of treatment is completed, assessment of pain level will continue 3 times daily with approximately 6 hours in between each assessment until the lesion is healed.

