### **7.13.4 Pain Severity**

For pain severity, counts and percentages will be summarized for all levels of severity, and Cochran-Mantel-Haenszel tests will be used to compare the groups.

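### Read literally, maximum pain severity includes a reading taken before the first treatment, and no pain analysis adjusts for baseline pain, which costs sensitivity on an 'other' efficacy endpoint

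*Protocol*

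**What the plan says.** **Endpoint.** Protocol 10.7.8 consists of one sentence: "The maximum severity (over time) of lesion pain will be summarized". The synopsis (Statistical Methods) names the test: "For pain, the maximum severity will be analyzed using the Cochran-Mantel-Haenszel Test to test for differences between treatment groups". Neither says when the period for the maximum begins.

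**Timing of readings.** Under Protocol 7.2.5, the diary assessments of stage and pain "are to be done three times per day, just prior to initiation of each treatment". Protocol 10.7.7 and SAP 6.1.4 keep this schedule; the SAP has the subject record, "just prior to each treatment and three times daily once treatment is complete, the level of pain caused by the defined lesion".

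**Baseline pain.** Protocol 7.2.5.1 has the clinic ask, at the call to enter the Treatment Phase, for the onset time of any pain "caused by the herpes lesion to be treated along with the severity of any lesion pain". With the first diary entry, that makes two possible pre-treatment scores.

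**Strata.** The main test is given without strata (Protocol 10.7; SAP 7.13.4: "Cochran-Mantel-Haenszel tests will be used to compare the groups"). Protocol 10.4 and SAP 7.2, 7.13 and the footnote to the 7.13.5 matrix add analyses by lesion stage at treatment start (Stage 1 or Stage 2). None uses baseline pain.

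**Protocol against SAP.** The SAP does not carry over the maximum. Section 6.1.4 defines only the rating scale, 7.13.4 summarises every severity level, and 7.13 compares groups at each visit. SAP 9 nevertheless says that no changes from the protocol analyses are planned.

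**The concern.** A subject who rates pain as severe just before the first application scores severe on this endpoint whatever happens afterwards. The maximum therefore mixes pain that treatment could have changed with pain that it could not. Randomization makes the pre-treatment part alike in both arms on average, so the mixture pulls the arms together.

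Pre-treatment pain is plausible here. Subjects wait through prodrome and start only at a visible Stage 1 or 2 lesion (Protocol 5.3, 7.2.1), and enrollment requires a history of prodromal symptoms in at least half of past episodes (5.2.1).

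What is at stake is the chance of seeing a real pain effect. Subject-assessed pain severity was one of the TR-H-211 trends that this trial follows up (Protocol 2 and 4).

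**Working it through.** **1. Plan's own figure.** There is none to reproduce. Protocol 10.7.9 and SAP 3 discuss power for classical lesion duration and the herpetic episode only.

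**2. Direction.** Let B be the pre-treatment score and P the maximum of later readings, each from 1 to 4. The literal endpoint is M = max(B, P). If B = 4, then M = 4 for every P. If B = 3 and treatment lowers P from 3 to 2, M is 3 either way, so a one-level benefit scores zero. In general |max(B, p1) − max(B, p0)| ≤ |p1 − p0|, so including B can shrink a benefit but cannot enlarge it.

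**3. Inputs from the documents.** At least 75 treated subjects per arm, 1:1 allocation (Protocol 4), four pain levels (7.2.5.1), two-sided 0.05 (10.4).

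**4. Assumptions, not in the documents.** Control post-treatment maximum none/mild/moderate/severe = 20/35/30/15%; drug effect δ = 0.5 SD on a latent normal scale; latent baseline-to-maximum correlation ρ = 0.3 or 0.6; three baseline pain distributions.

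**5. Model and test.** Latent baseline Z0 ~ N(0,1). Latent maximum Z1 = ρ·Z0 + √(1 − ρ²)·ε − δ·(1 if Merlin, 0 if placebo). Both are cut into four levels at the assumed percentages. The CMH row-mean-scores statistic over strata k is

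Q = [Σ(S_k − n1_k·ȳ_k)]² / Σ[(n1_k·n0_k/n_k)·s_k²],

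where S_k is the Merlin score total, ȳ_k the stratum mean and s_k² the stratum variance. Q is referred to 3.84 (1 df). The unstratified test uses one stratum. With 4,000 replicates the simulation error is at most √(0.25/4000) = 0.8 percentage points.

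**6. Results at 0.5 SD.**

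| Any pain at entry (none/mild/mod/sev %) | ρ | B above P | Mean difference shrunk by | Power, literal maximum | Power, post-treatment maximum | Power, post-treatment, stratified by B |
|---|---|---|---|---|---|---|
| 30% (70/20/8/2) | 0.3 | 9% | 14% | 69% | 82% | 83% |
| 30% | 0.6 | 5% | 10% | 71% | 80% | 89% |
| 55% (45/35/15/5) | 0.3 | 20% | 29% | 54% | 80% | 83% |
| 55% | 0.6 | 14% | 27% | 56% | 81% | 91% |
| 75% (25/35/28/12) | 0.3 | 36% | 49% | 32% | 81% | 82% |
| 75% | 0.6 | 31% | 51% | 28% | 81% | 91% |

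Example of the shrinkage, first row: mean difference 0.375 with the literal maximum against 0.438 with the post-treatment maximum, and 1 − 0.375/0.438 = 0.14.

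**7. Type I error.** With δ = 0 (3,000 replicates) rejection was 4.2–5.4% in every version.

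**8. Smaller effect, 0.45 SD.** Across assumed baseline distributions, power was 26–70% with the literal maximum, 71–76% with the post-treatment maximum and 74–80% when also stratified. With only 20% in pain at entry, it was 65–66% against about 72%.

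**9. Value of stratifying.** In a separate set of 0.45 SD runs, the unstratified post-treatment maximum gave 72–74%. Stratifying gave 72–73% at correlation 0.3 and 77–81% at 0.5. Most of the gain therefore comes from dropping the pre-treatment reading.

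**The case against.** - **Inclusion is inferred.** No sentence says that the pre-treatment entry counts, and whether the call value counts is not stated. This stands as a description. But a programmer who follows the protocol takes the maximum of all diary entries, and the first of these is pre-treatment by design.
- **A reader might infer that the CMH test has no strata at all.** The documents do not support that. Stage 1/Stage 2 analyses are planned, although the SAP footnote may mean two separate analyses. A single-stratum CMH test is also a valid two-arm comparison of ordered categories. What is absent is any use of baseline pain.
- **The SAP contains no maximum.** Under its by-visit comparisons an early pre-treatment reading would not carry forward to later visits. This is correct, and it limits the dilution to the protocol's endpoint. But SAP 9 declares no changes, so the two documents disagree on what will be analysed.
- **The size rests on assumptions.** This stands. A very low power figure needs many subjects whose single pre-treatment reading is worse than every later one: 31–36% in the 75% case. If few have pain at entry, the loss is modest.
- **Strata may be sparse.** Four pain levels combined with lesion stage would be thin at 75 per arm. This is answered by collapsing levels and not crossing the two factors.

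**Conclusion.** The point holds as a cheap improvement to an 'other' efficacy endpoint. Read literally, the protocol's maximum takes in a reading that the drug could not influence, and a baseline pain score is collected but not used as a stratum or covariate in any pain analysis.

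The direction follows from the definition. The size does not, because the documents give no pain distribution, effect size or correlation. As an illustration with 75 per arm and 0.45–0.5 SD, power goes from about 71–82% to about 60–71% when 20–30% have pain at entry, and to about 26–32% when 75% do.

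Three stronger readings should not be drawn. This is not a false-positive problem: type I error stays near 5%. It does not touch the primary endpoint. And no single power figure can be attributed to the plan. Subject-assessed pain severity is listed under other endpoints in the synopsis, Protocol 10.2.1 and SAP 6.1.3. Protocol 10.2.1 also lists a clinician-assessed version as secondary, which the SAP does not carry over.

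**What to change.** 1. Define pain severity as the subject's maximum over diary readings after the first application. Put this in Protocol 10.7.8 and in SAP 6.1.4 and 7.13.4, and state that the by-visit comparison in SAP 7.13 does not apply to it, so that the documents agree.
2. Run the main test as a CMH row-mean-scores test stratified by pre-treatment pain: the first diary entry, or the call value if that entry is missing (Protocol 7.3.2 bars later completion). Collapse sparse levels, for example to none, mild and moderate-severe.
3. Keep the Stage 1/Stage 2 analyses as planned.
4. Report pre-treatment pain by arm with the baseline characteristics (SAP 7.4).

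**Cost.** Wording only, settled before unblinding; the data are already collected. Subjects with no post-treatment reading leave this endpoint and should be counted by arm.
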